### **Background and rationale**

Physical activity in COPD patients is reduced, (1) and this inactivity is associated with poor outcome, including increased health care utilization and mortality. (2-5) Bronchodilators, considered a first line therapy of COPD, have documented effectiveness in physiologic function, symptom relief, and exercise capacity enhancement, but apparently do not consistently increase in physical activity. Even pulmonary rehabilitation exercise training, with remarkable effectiveness in increasing exercise capacity, does not consistently increase physical activity.(6, 7) There are probably multiple reasons behind this apparent lack of efficacy, but two important ones are a poor signal-to-noise ratio in accelerometers (used to measure activity) and real problems translating increases in physiologic function (such as increased FEV1 or six minute walk distance) into increases in physical activity. Both of the above are major areas of interest that need to be addressed to improve our care of COPD.

This study will follow physical activity following pulmonary rehabilitation longitudinally over 48 weeks. We will use a state-of-the-art accelerometer, the DynaPort (<https://www.mcroberts.nl/products/movemonitor>), to analyze minutes walking per day

as the primary outcome, rather than vector magnitude units (VMU) or estimated steps per day. The DynaPort device was rated favorably by PROactive COPD (<http://www.proactivecopd.com>) which tested accelerometers. Additionally, there is too much variability in VMU, and estimated steps per day in slow moving COPD patients are inaccurate. Minutes per day of walking activity appears to be a more useful outcome. Walking activity from the DynaPort has been demonstrated to be very responsive to exercise training in lung transplant patients. (8) Finally, more information is needed to determine the factors that influence the translation of exercise capacity gains realized in the rehabilitation center into increased physical activity in the home and community settings. One editorial commented that it takes 3 months to train the muscles and 6 months to train the brain.(9) We will explore potential factors influencing this important outcome, including baseline activity levels, demographic variables, changes in exercise capacity, psychological variables, and self-efficacy scores. Finally, we will evaluate the rate of change (trajectory) in physical activity over approximately six months after the pulmonary rehabilitation intervention. There are limited data suggesting it takes time for the translation of increased exercise capacity into increased physical activity to occur. (10) If our study corroborates these findings, it would potentially influence our therapeutic approach to the physically inactive COPD patient.

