#### Predictors of *change* in physical activity

5. Exploratory: We will be able to identify responders versus non-responders with respect to: 1) the change in activity at 12 weeks, and 2) the trajectory (over 48 weeks) in these activity measurements; this will include the slopes of change in physical activity. We will then relate baseline variables to responder status. We cannot a priori determine a threshold for physical activity responder status; this will have to be done a posteriori when data are available. We anticipate from the post-lung transplant study the responder threshold will be an increase in 10 minutes walking time per day. Predictor variables are listed above.

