### Sample size estimates

Sample size estimates are based on Langer et al. Am J Transpl 2012 and using <http://www.biomath.info/power/ttest.htm>. Patients following lung transplantation were randomized to exercise training or standard care. Walking activity (min/day) from baseline to 12 weeks increased from  $36 \pm 16$  to  $56 \pm 24$  in the treatment group. Assuming a treatment difference, in minutes, of 18 and a SD of 20 and a within-group analysis, an n of ~ 12 would have a power of 0.80 to show this difference. We expect our improvement in walking time with rehabilitation in COPD patients will be less robust. Assuming an increase in activity (minutes per day of walking) of 10 minutes would require an n of 34 to give a power of 0.80, but an improvement of 8 minutes would require 52 patients. Forty evaluable patients appears to be a reasonable number.

Number of subjects: Our goal will be to recruit 40 patients with evaluable data at 12 weeks. Assuming 10 dropouts during rehabilitation, we would need to recruit 50.

Study period: Recruitment over the 6 sites will be over 10 months (~ 40 weeks). Since study follow-up is for 48 weeks per patient, the study will last approximately 84 weeks from first patient in to last patient out.

Activity measurement: We will use the DynaPort MoveMonitor to assess: sedentary activity, upright activity, walking activity, activity intensity, and steps per day. Activity will be measured for 7 consecutive days, 3 days (12 hours per day) minimum. Patients will be asked to wear the devices 24 hours per day, if possible.

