### Data analysis

The primary variable to be assessed will be changes in daily walking activity (in minutes) from baseline to week 12. The statistical approach for this will be a repeated measures analysis of variance using SAS. Covariates may be added, if necessary. We anticipate day of week variation (Sundays have less activity) and seasonal variation (less activity in winter). This will be handled by including these variables as covariates in the analysis. We will also analyze the 24 36 and 48 week endpoints compared to baseline this way. Trajectory changes will be first analyzed by graphs relating activity (in minutes) at each data collection time. We will also analyzed slopes of activity, it possible. Responder non-responder analyses will be performed using logistic analysis with demographics and baseline disease characteristics as potential predictor variables.

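### If baseline activity is examined as a factor in the activity gain, measurement noise alone favours the least active patients, and the plan neither settles whether it enters the model nor guards against this

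*Combined protocol and SAP*

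**What the plan says.** The Background and rationale lists what will be studied as influencing the step from exercise-capacity gain to more activity at home: "We will explore potential factors influencing this important outcome, including baseline activity levels, demographic variables, changes in exercise capacity". Baseline activity comes first. The Design section makes predictors of change in activity one of three types of analysis.

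Hypothesis 5, under Predictors of change in physical activity, defines responders by the 12-week change and by the 48-week trajectory, and continues: "We will then relate baseline variables to responder status". The cut is to be set once data are available, with the expectation that "the responder threshold will be an increase in 10 minutes walking time per day". On which variables, it says only "Predictor variables are listed above". The list above it is the one under Predictors of baseline physical activity (hypothesis 4), where baseline activity is the outcome and not one of the listed variables.

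Data analysis states: "Responder non-responder analyses will be performed using logistic analysis with demographics and baseline disease characteristics as potential predictor variables". Baseline activity is not named there either. Day of week and season are to be covariates in the activity analyses. Regression to the mean, reliability of the activity measure and a repeat baseline recording are not mentioned. There is no control group.

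**The concern.** Write B for recorded baseline walking, F for recorded follow-up walking and D = F - B. Each recording is a mean over three to seven days and differs from the patient's usual level by some error. A patient whose baseline week happened to be quiet has a low B and, for that reason alone, a high D. The baseline error therefore produces a negative association between B and D when usual activity and true gain are unrelated.

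Putting B into the model as a covariate does not cure this for B's own coefficient: the slope of D on B is the slope of F on B minus 1, and carries the same error.

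The setting gives the noise room to matter. The Background itself cites a poor signal-to-noise ratio in accelerometers, three days are accepted as an assessment, there is one baseline recording, and no untreated group shows how much regression to the mean to expect. At stake is a false statement that the least active patients respond best, in a study that lists predictors of response among its main aims.

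**Working it through.** **Inputs from Sample size estimates.** SD of change 20: "Assuming a treatment difference, in minutes, of 18 and a SD of 20 and a within-group analysis". Walking-time SD 16 at baseline and 24 at 12 weeks, from the treated arm of the cited transplant trial. Assumed COPD gain 10 min/day. Target 40 evaluable patients.

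**Assumptions.** Reliability R of the baseline mean 0.9 to 0.6; equal error variance at both visits; normal distributions; usual activity unrelated to true gain; two-sided 0.05.

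**The plan's own figures.** An increase "of 10 minutes would require an n of 34 to give a power of 0.80". A paired t-test with SD 20 and two-sided 0.05 gives n = 12, 34 and 52 for gains of 18, 10 and 8 minutes, matching the plan's three numbers. So 20 is being used as the SD of within-patient change.

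**Spurious association.** Only the baseline error is shared by B and D, with opposite sign:

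- cov(B, D) = -(1 - R) × 16² = -(1 - R) × 256
- slope of D on B = -(1 - R)
- correlation = -(1 - R) × 256 / (16 × 20) = -0.8 × (1 - R)

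Responder shares (gain of at least 10 min/day) and rejection rates are by simulation.

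| R | slope | correlation | responders, lowest v highest baseline third | p<0.05 at n = 40 |
|---|---|---|---|---|
| 0.9 | -0.10 | -0.08 | about 54 v 47% | about 8% |
| 0.8 | -0.20 | -0.16 | about 57 v 43% | about 17% |
| 0.7 | -0.30 | -0.24 | about 60 v 40% | about 33% |
| 0.6 | -0.40 | -0.32 | about 64 v 36% | about 53% |

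With no true link, the rejection rate should be 5%.

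**Where the cited SDs fall.** With SDs 16, 24 and 20, cov(B, D) = (24² - 16² - 20²)/2 = (576 - 256 - 400)/2 = -40. The correlation is -40/(16 × 20) = -0.125 and the slope -40/256 = -0.156. With no true link this corresponds to R = 1 - 0.156 = 0.84. A correlation of -0.125 reaches p<0.05 in about 12% of samples of 40.

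**A less favourable assumption.** If everyone had the same true gain and the SD were equal at both visits, the correlation would be -√((1 - r)/2), with r the correlation between visits. For r = 0.9, 0.7 and 0.5 this is -0.22, -0.39 and -0.50, significant in about 28, 70 and 92% of samples. This sits less well with the plan's figures, since the cited SD rises from 16 to 24.

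**Correcting the slope.** If β is the slope of true gain on usual activity, the observed slope is b = Rβ - (1 - R), so β = (b + 1 - R)/R. For b = -0.156:

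- R = 0.9: (-0.156 + 0.10)/0.9 = -0.06
- R = 0.8: (-0.156 + 0.20)/0.8 = +0.06 (rounded)
- R = 0.6: (-0.156 + 0.40)/0.6 = +0.41

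The sign depends on R, so a range must be reported. For given R the standard error is divided by R, that is, multiplied by 1.11 at 0.9 and 1.67 at 0.6.

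**Why not Oldham's method.** Relating D to (B + F)/2 has covariance (var F - var B)/2, which is positive whenever follow-up variance rises because true gains differ between patients. At R = 0.9, var F = 256 + 400 - 2 × 25.6 = 604.8, so the covariance is (604.8 - 256)/2 = 174.4. The variance of the average is (256 + 604.8 + 2 × 230.4)/4 = 330.4, and the correlation is 174.4/(20 × √330.4) = +0.48. At R = 0.8, 0.7 and 0.6 it is +0.43, +0.37 and +0.31. With no true link, about 90, 80, 66 and 49% of samples of 40 are falsely significant. The cited SDs alone give +0.45.

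**The case against.** The strongest objection is that the plan may never fit this model. Baseline activity appears as a factor only in a Background sentence; hypothesis 5 points to a list without it, and Data analysis restricts the responder model to demographics and baseline disease characteristics. This stands. A reader might infer that baseline activity is a specified predictor in the responder model; the operative sections do not say so. What remains is a stated intention to explore it, and nothing that rules it in or out.

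Second, the size depends on a reliability that the documents do not give. At 0.9 the artefact is small, and the day-of-week and season covariates may remove some noise. This also stands. A reader might infer that the study will report the least active as best responders. The figures support only an expected direction, with a chance of a significant result that ranges from slight to about one in two.

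Third, the study calls itself predominantly hypothesis-generating, hypothesis 5 is labelled exploratory, and the plan concedes that the lack of a control group limits its conclusions. That lowers the stakes but does not remove the bias, since the label does not tell a reader that the expected result under no effect is other than zero. A reader might also infer consequences for who is referred; nothing in the documents ties referral to this analysis.

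**Conclusion.** The point holds in limited form. The plan says baseline activity will be explored as a factor in the gain, leaves it out of the lists that govern the analysis, and has no safeguard against the negative association that noise in the shared baseline creates. Under baseline SD 16, change SD 20, mean gain 10, equal error variance at both visits and reliability 0.9 to 0.6, the spurious correlation is -0.08 to -0.32, with a false-positive rate of about 8 to 53% at n = 40. The SDs come from a transplant trial, and the reliability range is an assumption. The direction does not depend on these values so long as reliability is below 1 and there is no true link; the size does. The primary 12-week comparison of mean walking time, and its sample size, are not affected.

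**What to change.** 1. State under Predictors of change in physical activity and Data analysis whether baseline walking enters the change and responder models, and bring the Background into line.
2. If it enters, use it for adjustment only. Do not interpret its raw coefficient, odds ratio or tertile contrast.
3. If the question of a baseline effect is kept, report the slope of change on baseline corrected for measurement error, β = (b + 1 - R)/R, with its interval. Estimate within-visit error from the day-level DynaPort values, allowing for the number of valid days. Those values do not show week-to-week variation, so cover it with a range of reliability stated in advance.
4. Claim a baseline effect only if it exceeds what regression to the mean produces across that range, that is, an uncorrected slope of -(1 - R).
5. Do not use Oldham's method, because true gains are expected to differ between patients.

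The cost is a few sentences in the plan, one extra calculation on data already being recorded, and a wider interval for the baseline effect. No added visits, patients or change in sample size are needed.

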### **Design:**

This will be predominately a hypothesis-generating study. Its general design is that of a longitudinal study (without a control group) evaluating directly-measured physical activity in COPD patients who had participated in pulmonary rehabilitation. Activity measurements will be at baseline (before exercise training is started), and at approximately 12, 24, 36, and 48 weeks (+/- 3 weeks at each time period) following pulmonary rehabilitation. There will be no direct change, per protocol, in the patient's pharmacological treatment for COPD (controller or rescue inhaler medication) or other medical problems; this treatment will be directed by the patient's health care provider.

Three distinct types of analysis will be performed:

1. Evaluation of changes in physical activity before and after pulmonary rehabilitation

2. Predictors of baseline physical activity
3. Predictors of *change* in physical activity following pulmonary rehabilitation.

This will be an intent-to-treat analysis, providing patients complete 50% or more of the pulmonary rehabilitation sessions. Those dropping out with less than 50% attendance will be dropped from the study.

Dealing with Exacerbations: It is anticipated that patients will have COPD exacerbations over the course of the study. Since exacerbations themselves affect physical activity, activity testing will be postponed for 2 weeks following the clinical end of the exacerbation. We have determined that physical activity returns to close to baseline by two weeks after the exacerbation (Ehsan et al, A Longitudinal Study Evaluating the Effect of Exacerbations on Physical Activity in Patients with Chronic Obstructive Pulmonary Disease. Annals of American Thoracic Society 2013; 10(6):559-64). If two exacerbations occur within the same time block, testing for that period will not be performed, and the last observation will be carried forward. If a patient is hospitalized for an exacerbation, that patient will be dropped from the study.

Comment: We will not be altering the pharmacological management of the patient; this study will focus only on the pulmonary rehabilitation component and specifically how it affects physical activity. It is currently almost impossible to carry out a randomized, controlled trial of pulmonary rehabilitation, since the intervention is considered a gold standard of therapy. The within-group analysis without a control group would be feasible and would not raise ethical issues. While this approach (without a control group) limits the strength of conclusions, the primary intent of this analysis is to explore the rate of change in physical activity with pulmonary rehabilitation (realizing that it probably takes longer to improve than exercise capacity) and predictors of response to the intervention.

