**Hypotheses to be tested:**

Changes in activity following pulmonary rehabilitation

1. Compared with baseline, COPD patients participating in outpatient pulmonary rehabilitation will show an increase in directly-measured physical activity

- (minutes per day of walking activity from the DynaPort) at the  $12 \pm 3$  week assessment. (primary hypothesis)
2. Compared with baseline, COPD patients participating in outpatient pulmonary rehabilitation will show increases in upright activity, activity intensity, steps per day, minutes with METs  $> 2$  (from the DynaPort) after  $24 \pm 3$ ,  $36 \pm 3$  and  $48 \pm 3$  weeks
  3. Exploratory: We will analyze the trajectory of physical activity over the 48 weeks after initiating pulmonary rehabilitation.

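### The analysis is called intent-to-treat but is limited to patients with at least 50% attendance and no hospitalization for an exacerbation, and the plan does not say whether recordings made before a drop are kept

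*Combined protocol and SAP*

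**What the plan says.** The Design section sets the analysis population in two sentences: "This will be an intent-to-treat analysis, providing patients complete 50% or more of the pulmonary rehabilitation sessions", and "Those dropping out with less than 50% attendance will be dropped from the study". Under its heading on exacerbations it adds: "If a patient is hospitalized for an exacerbation, that patient will be dropped from the study". Two exacerbations in one time block are treated differently: "testing for that period will not be performed, and the last observation will be carried forward".

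The primary hypothesis is that "COPD patients participating in outpatient pulmonary rehabilitation will show an increase in directly-measured physical activity" at the week-12 assessment. The trajectory and predictor analyses are labelled exploratory, although the comment closing the Design section says "the primary intent of this analysis is to explore the rate of change in physical activity with pulmonary rehabilitation", together with predictors of response. For the responder analysis the plan says: "We will then relate baseline variables to responder status".

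The comments in the Protocol synopsis apply carry-forward to missing observations in general. They give examples in an open-ended list and do not mention dropped patients. The Data analysis section names repeated measures analysis of variance, but no analysis set, neither drop rule and no sensitivity analysis. Sample size estimates aims for 40 patients evaluable at week 12 out of 50 recruited, allowing for 10 dropouts during rehabilitation.

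**The concern.** An intent-to-treat set is fixed by entry to the study. This one is fixed by two things that happen later: adherence to the program and a clinical event. The label and the rule therefore conflict within one paragraph. A reader who sees the label will take the result to apply to everyone who starts rehabilitation.

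There is no control group against which selection could show. The Background section says "this inactivity is associated with poor outcome, including increased health care utilization and mortality", so removal on hospitalization may be related to the quantity being measured. That statement concerns activity level, not change in activity, so it does not tell us which way any bias would run.

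The silence on earlier recordings is a separate gap. Two analysts following this plan could include different patients at baseline, at week 12 and along the trajectory.

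**Working it through.** **1. The plan's own figures.** Inputs from Sample size estimates: SD of change 20 min; gains of 18, 10 and 8 min; power 0.80. Two-sided alpha of 0.05 is my assumption, as none is stated. A paired t-test with the exact noncentral t gives n = 12, 34 and 52, as in the plan. Recruitment: 40/(1 − 10/50) = 50, also as in the plan. The sample size arithmetic is not at fault, and the point does not depend on it.

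**2. When the conditions arise.** The baseline recording is made before exercise training starts. Attendance and hospitalization are known only afterwards, so both conditions are post-baseline.

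**3. Which analyses each rule reaches.**
- Below 50% attendance: the patient is out of the analysis by the plan's own condition.
- Hospitalized before the week-12 recording: no week-12 value exists, so the patient is out of the primary comparison unless baseline is carried forward.
- Hospitalized after week 12: the primary result changes only if earlier recordings are deleted. The later visits lose the patient unless values are carried forward.

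**4. Week-12 illustration.** The documents give no outcomes for dropped patients, no split of the 10 dropouts by reason and no hospitalization rate. Assume that 40 retained patients gain 10 min on average and that k removed patients have zero change on average. The mean over all patients is 40 × 10/(40 + k):
- k = 2: 400/42 = 9.5 min
- k = 5: 400/45 = 8.9 min
- k = 10 (every expected dropout): 400/50 = 8.0 min

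**5. Would week-12 significance change?** In the 40 retained patients SE = 20/√40 = 3.162 and t(39) = 2.023, so the 95% CI is 10 ± 6.40, or 3.6 to 16.4 min. Now include the k removed patients with mean change m, keeping SD 20 within each group. With n = 40 + k and w = k/n:
- mean = (400 + k·m)/n
- SD = √(400 + w(1 − w)(10 − m)²)

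For k = 10 and m = 0, SD = √(400 + 0.16 × 100) = 20.4, SE = 20.4/√50 = 2.88 and t(49) = 2.010. The CI is 8.0 ± 5.8, or 2.2 to 13.8 min, still above zero.

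The lower limit reaches zero only when m is about −9.5 min (k = 10), −20 min (k = 5) or −47 min (k = 2). If baseline walking were near the 36 min/day of the transplant study used for sizing (an assumption for this population), the k = 2 value could not occur.

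**6. Trajectory illustration.** Assume 4 of 40 patients are hospitalized after week 12, had zero change at week 12 against 10 min in the other 36, and nobody changes afterwards.
- Earlier data deleted: 10 min at every visit.
- Earlier data kept, simple averages of what is available: (36 × 10 + 4 × 0)/40 = 9.0 min at week 12, then 10 min. This is a rise of 1.0 min that no patient had.
- With 2 or 8 such patients the false rise is 0.5 or 2.0 min. If their week-12 change was 5 min, these rises halve. If they had gained more than the others, the sign reverses.
- A likelihood model using the kept week-12 data gave later means of 9.02 to 9.24 min against a true 9.0, in a large simulation with assumed per-visit noise SD of 0 to 10 min.

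**The case against.** The strongest reply has four parts.

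- **The attendance condition is open.** It stands in the same sentence as the label and fits a hypothesis about patients participating in rehabilitation. This stands: on attendance, what is wrong is the label. It does not cover hospitalization, because a patient can participate fully and be hospitalized later.
- **The exacerbation handling has a stated reason.** The Design section notes that exacerbations affect activity, and moves from postponing, to carrying forward, to dropping. That is a legitimate choice of what to estimate, but it has to be described as such. It does not tell the analyst what to do with recordings made before the event.
- **The text leans toward keeping week-12 data.** A reader might infer that a patient hospitalized after week 12 also vanishes from the primary estimate, because a classical repeated measures analysis of variance over all visits omits incomplete patients. The documents do not support taking that as the plan. Data analysis defines the primary variable as change from baseline to week 12 and compares each later visit with baseline in the same way. The sample size counts patients evaluable at week 12. The point is silence, not planned deletion.
- **The study is single-arm and mainly hypothesis-generating.** No randomized comparison is broken. This stands and limits the seriousness, but there is a stated primary hypothesis and a label that tells readers whom it covers.

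A reader might also infer that carry-forward covers dropped patients. The open-ended list of examples allows that, but the Design section treats carrying forward and dropping as separate outcomes, so it is unlikely to be meant.

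**Conclusion.** The label is wrong as written. The set is of per-protocol type, and its results describe patients who attend at least half the sessions and are not hospitalized for an exacerbation. The fate of earlier recordings is not stated in Design, Protocol synopsis or Data analysis.

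The size cannot be derived from the documents. Under the extreme assumption that all 10 expected dropouts are removed by these rules and have zero change, the week-12 gain falls from 10 to 8 min. With fewer such removals it falls less. Week-12 significance is unlikely to change, so the issue there is how large the gain is and whom it describes. The exploratory week 24 to 48 trajectory and the responder analyses are most exposed. The illustrated trajectory artefact is 0.25 to 2.0 min, small against an SD of 20, and rests wholly on assumed numbers.

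It is tempting to say that the plan inflates the gain. The documents do not support that, because they give no outcomes for dropped patients and the link they cite concerns activity level. The direction is unknown. This should be fixed, mainly because the fix is cheap.

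**What to change.** 1. Delete the intent-to-treat label. Call the set with at least 50% attendance and no exacerbation hospitalization per-protocol, limit its conclusion to those patients, and report removals by reason.
2. Also analyse all enrolled patients who start rehabilitation and have a valid baseline recording. Use every recording already obtained, including those made before a drop, in a likelihood-based repeated-measures model. Do not delete earlier visits because of a later hospitalization.
3. Reconcile the two drop sentences in Design with the carry-forward rule in the Protocol synopsis, and say whether carry-forward applies to dropped patients.
4. Add a simple sensitivity analysis, such as the tipping point in step 5 of the working, for patients with no post-baseline recording. The model assumes missing at random and cannot recover their outcomes.

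Further recordings after a drop are optional, since they need extra resources. The cost is protocol wording, a little more analysis work and possibly a smaller reported gain.
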